## **11.0 Number of Participants**

### **11.1 Number of Participants to be Consented:**

We expect to enroll approximately 300-350 PCPs in both the baseline and follow-up web surveys.

We expect that 400-450 PCPs will be included in the final analytic samples for the analysis of EHR data and PDMP data.

We expect that 20,000 charts will be reviewed in the retrospective chart reviews of primary care visits with current opioid users.

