#### *Primary Outcome Analysis*

To test our primary hypotheses, we will fit mixed effects logistic regression models using data from the 12-month pre-intervention period, and the post-intervention period prior to any second-stage randomization (the model for the current “high risk” opioid group will be multinomial logistic regression due to the 3-category outcome). All models will include fixed effects for whether the encounter was at an intervention arm clinic, an indicator for whether the measurement was after the interventions began, and their interaction. The interaction is the primary measure of the intervention effect. These models include random effects for clinic and PCP (nested in clinic) to account for within-clinic and within-provider correlation. Because of the cluster-randomized design with a moderate number of clinics, residual imbalances in patient and PCP-characteristics among the randomized groups may exist. The primary analysis model will adjust for characteristics at all levels of the hierarchy including clinic-level (indicators for the four systems), PCP-level (clinician type [MD/DO, NP, or PA], sex, and length of tenure in medicine), and patient-level (age, sex, race/ethnicity, insurance status, and in-person or virtual visit). Separate models will be fit to assess the PDMP integration and choice architecture intervention and for the opioid-naïve and current, high-risk opioid users. In each model, the intervention group pools across two arms of the factorial design (e.g., the choice architecture intervention pools across arms 2 and 4) and the control condition pools across the remaining two groups (e.g., arms 1 and 3 to continue the example). A Bonferroni correction will adjust inference for multiple comparison across two different populations (opioid naïve and current, high-risk opioid users) but we will not adjust for multiple tests across the two different interventions.

As an exploratory analysis, we will assess whether PCP characteristics (clinician type and tenure in medicine) and patient characteristics (age, sex, and race/ethnicity) moderate the interventions’ effect. Tests for treatment effect heterogeneity will be implemented by adding the interaction between the potential moderator and the intervention indicator to the models for the primary

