#### *Secondary Outcomes Analysis: PDMP and Web Survey data*

For other EHR-derived secondary outcomes, we will use the same general modeling framework as for the primary outcome but will fit mixed effects logistic or linear models depending on whether the outcome was categorical or continuous.

To assess intervention effects on the frequency of checking the PDMP we will fit mixed effects Poisson regression models using data from the 12 months pre- and post-intervention. All models will include fixed effects for whether the PCP was at an intervention arm clinic, indicator for whether the month was during the intervention period, and their interaction. The models will adjust for clinician type, length of tenure in medicine, and health system indicators, and include random effects for clinic and PCP (nested in clinic) to account for within-clinic and within-provider correlation. As an exploratory analysis, we will assess whether PCP characteristics (clinician type and length of tenure) moderate the effect of the interventions using a similar process as the primary outcome.

A similar approach will be used for the web survey data, except we will fit mixed effect linear regression models using data from the pre- and post-intervention surveys. All models will include fixed effects for whether the PCP was at an intervention arm clinic, an indicator for whether the survey was the 12-month follow-up, and their interaction.

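### PCP web survey: the planned arm-by-wave interaction is valid but less precise than an analysis of the 12-month score adjusted for the pre-activation baseline score

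*Combined protocol and SAP*

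**What the plan says.** Section 3.2 lists PCP satisfaction with decision support as a secondary outcome, measured by web surveys at the start and end of the 12 months. For these data, Section 17.3 (Secondary Outcomes Analysis: PDMP and Web Survey data) specifies a linear mixed model with an intervention-clinic indicator, "an indicator for whether the survey was the 12-month follow-up, and their interaction". No model conditions on the baseline score or constrains the arms to share a baseline mean. On size, Section 11.1 says: "We expect to enroll approximately 300-350 PCPs in both the baseline and follow-up web surveys". No power figure is given for the survey.

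The EHR and PDMP models have the same form. The primary EHR model has "fixed effects for whether the encounter was at an intervention arm clinic, an indicator for whether the measurement was after the interventions began", plus their product, and "The interaction is the primary measure of the intervention effect". Its correlation structure is "These models include random effects for clinic and PCP (nested in clinic"). For other EHR outcomes, "we will use the same general modeling framework as for the primary outcome". The PDMP model is a mixed Poisson regression with the same three terms.

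On survey timing, Section 12.1 has two invitations before activation and a third one day after it. The same section says that PCPs in the intervention arms are informed of what their clinics will receive.

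**The concern.** With arm, wave and arm-by-wave all free, the interaction among complete pairs is the between-arm difference in mean change. Clinics are randomised (Section 5.1), so the expected arm difference before activation is zero, unless response differs by arm. An observed baseline difference is then chance, and only a fraction r of it should reappear at 12 months. The planned model removes all of it, which adds noise without removing bias.

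At stake is the precision of a secondary outcome with about 300-350 respondents, one score per wave and no stated power. The trial already collects the baseline that would recover part of that precision.

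**Working it through.** **Plan's own figure.** The survey has none, so I reproduce Exhibit 8 to show that the calculation matches the planned type of model. Inputs (Section 17.2 and Exhibit 8): 12 v 12 clinics, 10 PCPs per clinic, a 7% rate, 6 post-months, two-sided 0.05. The 12 pre-months are from Section 17.3. Random intercepts cancel in the interaction, so on the log-odds scale the variance is 3/(p(1 - p)m)/120, with m = 6 x visits per month. A 15% reduction is 0.1737 in log odds.
- 30 visits: variance 0.002133, SE 0.0462, power 96.4% (stated 96%).
- 15 visits: variance 0.004267, SE 0.0653, power 75.8% (stated 76%).

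**Survey.** Assumptions: complete pairs, equal variances, 48 clinics x 7 PCPs = 336 (inside 300-350), split 168 v 168 as in the pooled two-arm contrast. The correlation r is not in the documents.

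Without clinic correlation, the per-PCP variance is 2(1 - r) for the change score and 1 - r² after adjustment. The ratio is (1 - r²)/(2(1 - r)) = (1 + r)/2.

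With a clinic ICC of 0.025 (the clinic correlation of Section 17.2, borrowed for the survey), replace r by the correlation of clinic means, R = (0.025 + (r - 0.025)/7)/(0.025 + 0.975/7). At r = 0.5, R = 0.0929/0.1643 = 0.565 and the ratio is 0.783.

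| r (assumed) | ratio, ICC 0 | ratio, ICC 0.025 | variance reduction |
|---|---|---|---|
| 0.4 | 0.70 | 0.74 | 26-30% |
| 0.5 | 0.75 | 0.78 | 22-25% |
| 0.7 | 0.85 | 0.87 | 13-15% |

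At r = 0.5 the planned SE is sqrt(2 x 0.5 x 2/168) = 0.109 SD. The difference detectable with 80% power is 2.80 x 0.109 = 0.306 SD. After adjustment it is 0.265-0.270 SD.

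**EHR models.** With ICCs 0.025/0.075 on the logistic scale, the total variance is (π²/3)/0.925 = 3.557, and the clinic-mean intercept variance is G = 0.0889 + 0.1778/10 = 0.1067. Let e0 and e1 be the pre- and post-period sampling variances per clinic. The free-arm variance is e0 + e1; the constrained one is G + e1 - G²/(G + e0). For 7% and 30 visits, e0 = 0.00427 and e1 = 0.00853, giving 0.01280 v 0.01264, ratio 0.987. The other Exhibit 8 and 9 visit rates give 0.975 (7%, 15 visits), 0.983 (17%, 10 visits) and 0.967 (17%, 5 visits). The reduction is therefore 1.3-3.3%. Exhibit 8 power would move from 96.4% to 96.6% and from 75.8% to 76.8%.

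**PDMP model.** The same formula on the log scale needs inputs that the documents do not give. I assumed 2-20 checks a month, PCP variance 0.25-1, clinic variance about a third of PCP variance and 7 PCPs per clinic. The ratio is 0.976-0.9996. Only with no clinic variation at all, and at the lowest corner (2 checks, variance 0.25, 12 post-months), does the gain reach 7%: R = 0.25/(0.25 + 1/24) = 0.857, ratio 0.929.

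**The case against.** **The planned analysis is not wrong.** This stands. The interaction is unbiased under randomisation, and no contradiction or type I error problem is shown. The point concerns efficiency only.

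**Where the gain is largest, the equal-baseline assumption is weakest.** This stands in part. Clinics were randomised, but respondents choose to answer, intervention-arm PCPs may know their arm, and some baselines may be completed after activation. If responders differ by b and the difference persists, the adjusted estimate (follow-up difference minus r times baseline difference) is biased by (1 - r)b. For b = 0.2 SD that is 0.14, 0.10 and 0.06 SD at r = 0.3, 0.5 and 0.7. The variance saved is (1 - r)² x 2/168 and the squared bias is (1 - r)²b², so in mean squared error they balance at b = sqrt(2/168) = 0.11 SD, whatever r is (0.12 SD with ICC 0.025). A persistent selection difference above that would favour the planned model.

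Several facts limit the risk without excluding it. All PCPs in all arms are invited, two of three invitations precede activation, the payment is the same for all (Section 12.5), and 75% response is expected (Section 26.1). The interaction also needs an assumption, namely that any responder difference is constant across waves. A baseline completed after activation can distort either model.

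**A reader might extend the criticism to the primary EHR and PDMP analyses, which share the model form.** The documents do not support that. Each PCP contributes many pre-period visits or months, so under the planned random intercepts the constrained EHR model would still give the baseline difference a weight of 0.90-0.96, close to a change score. EHR gains of 6-16% can be computed by assuming a between-period correlation of 0.9-0.7, but obtaining them needs a clinic-by-period random effect that the plan does not have. For 7% and 30 visits at correlation 0.8, optimal weighting saves 10.6% (0.0555 v 0.0496); dropping the arm term under the planned random effects saves 3.3%. In addition, PDMP data come only from PCPs who authorise access (Section 18.3), and nothing places that authorisation before allocation.

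**Conclusion.** The point holds for the web survey only, as an inexpensive gain in precision and not as an error. Over r = 0.4-0.7 the gain is 13-30% of the variance. It rests on an assumed r, complete pairs, equal variances and equal expected baseline means among responders. Selective response is a real downside, which is why the interaction model should still be reported. The change-score description is exact for balanced linear data and only approximate for the logistic and Poisson models. For those, a gain of about 1-3% or less on the inputs above does not justify a change.

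**What to change.** In the survey paragraph of Section 17.3:

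1. Make the main analysis a linear mixed model of the 12-month score on arm, with the pre-activation baseline score as covariate and a clinic random effect. Alternatively, use the constrained-baseline model (wave and arm-by-wave, no arm main effect, clinic and PCP random effects), which is essentially equivalent for complete pairs and also keeps PCPs with one wave.
2. Use only baseline surveys completed before activation, and treat later ones as missing.
3. Report response by arm, and completion date relative to activation.
4. Keep the planned interaction model as a sensitivity analysis, and comment if the two disagree.

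Leave the EHR and PDMP models as they are. The cost is SAP wording and one extra model fit, with no new data. The change should be fixed before the survey outcomes are analysed by arm; if that has already happened, label the adjusted analysis as post hoc.

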#### All PCPs, including visits with opioid-naïve and current opioid-using patients:

- 1) The frequency with which PCPs check the PMP.
- 2) PCP satisfaction with decision support

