### Exhibit 6. View of the PMP reminder

The study team will collect four types of data.

- 1) Passively-collected data from the Fairview and UMP EHR systems. These data involve no interactions with the participants, and is information that is already collected by Fairview IT as part of the EHR system.
- 2) Retrospective chart reviews of primary care visits with current opioid users. These chart reviews will involve no direct interaction with the study participants.
- 3) Passively-collected data from the Minnesota PMP. These data involve no interactions with the participants, and is information that is already collected automatically by the state of Minnesota.
- 4) Web survey data from participants. We will use the University of Minnesota's REDCap system to collect information from consenting primary care providers via web surveys. This will include basic demographic and background information, information about views on pain treatment and opioid prescribing, information about how providers interact with EHR systems, and information about satisfaction with clinical decision support for pain and opioid treatment. Web surveys will be fielded at the start and again at the end of the 12 month study period. All PCPs in the participating primary care clinics will be exposed to the study interventions their clinic is assigned to, regardless of whether PCPs complete the web survey or not.

[figure not shown]

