## 5.0 Procedures Involved

### 5.1 Study Design:

The study is a clinic-randomized trial of EHR clinical decision support tools for pain treatment and opioid prescribing. We propose clinic-level randomization in order to minimize the potential for spillovers or “contamination” of the intervention across the study arms.

The randomization plan is described in the figure below. There are two dimensions to the randomization. One dimension is treatment arm within a factorial study design: some clinics will be randomized to receive “care as usual,” (Arm 1), some clinics will be randomized to receive Intervention set A (Arm 2), some clinics will be randomized to receive Intervention B (Arm 3), and some clinics will receive both Interventions A and B (Arm 4). The other dimension to randomization occurs among the clinics that are assigned to Intervention set A or B, and involves those clinics being randomized to three different conditions. 1) The clinic receives the intervention set for the entire 12 month study period (Subarm A), 2) the clinic receives the intervention set for only the first 6 months of the study period, and then reverts to “care as usual,” for Intervention set A and PMP integration without the reminder function for Intervention B (Subarm B), or 3) The clinic receives the intervention set for the first 6 months, but in the second 6 months, Intervention set A will only fire in a random half of clinical encounters and the reminder function will only fire in a random half of clinical encounters for Intervention B (Subarm C).

Exhibit 7. Randomization plan

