### 5.3 Follow-Up:

At the end of the 12-month study period, participants will be invited to participate in a follow-up web survey that is similar in structure and length to the baseline survey.

The research team will also examine longer-term opioid prescribing patterns using the EHR data alone, up to 24 months after the completion of the study period.

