#### 5.5 Modifications to Procedures in Response to Data Monitoring Committee recommendations:

The external Data Monitoring Committee reviewed the results of the interim outcomes analysis (see Section 17.1 for details). Their letter to the PI is now added to the study IRB files. We will follow their recommendations and implement two changes to the study procedures.

Change #1: Open up the PMP Integration arm to the entire study population at the 6-month mark.

Change #2: We will not implement the secondary randomization of the intervention arm clinics into three subgroups. Instead, the clinics assigned to the “choice architecture” intervention set in Arms 3 and 4 will stay the same for months 6-12 of the study period.

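### The only follow-up survey falls at month 12, after PMP integration is opened to all clinics at month 6, so the planned survey interaction does not estimate PMP integration against no integration

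*Combined protocol and SAP*

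**What the plan says.** Section 3.2 lists "PCP satisfaction with decision support" as a secondary outcome for all PCPs. It comes from the web surveys. Section 4.1 fixes their timing: "Web surveys will be fielded at the start and again at the end of the 12 month study period". Section 5.3 repeats it: "At the end of the 12-month study period, participants will be invited to participate in a follow-up web survey". No intermediate wave is planned.

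The survey paragraph of Section 17.3 (Secondary Outcomes Analysis) specifies a mixed effects linear model on the pre- and post-intervention surveys. Its terms are intervention-arm clinic, "an indicator for whether the survey was the 12-month follow-up, and their interaction". It follows the approach of the other models. For the primary outcome, the same section pools two arms against the other two for each intervention and names the interaction as the main measure of effect.

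Section 5.5 reports the response to the Data Monitoring Committee: "We will follow their recommendations and implement two changes to the study procedures". The first is: "Open up the PMP Integration arm to the entire study population at the 6-month mark". This is current, adopted text.

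**The concern.** The PMP factor compares Arms 3 and 4, which have PMP integration from the start, with Arms 1 and 2, which begin without it. The survey model reads its effect at month 12. By then Arms 1 and 2 have had integrated access for about half the study, so the interaction no longer sets integration against its absence. Section 17.3 neither redefines the contrast nor warns about it.

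An analyst who follows the text exactly would report an early-versus-delayed comparison as the effect of the PMP intervention on satisfaction. A null result would then be read as showing that integration makes no difference to PCPs, and the trial has no comparator at month 12 to support that.

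**Working it through.** **Inputs**
- Survey waves: month 0 and month 12 only (Sections 4.1 and 5.3).
- PMP factor: Arms 3+4 against Arms 1+2 (arms from Section 5.1, pooling from Section 17.3). The survey paragraph does not name the arms, so I carry the pooling over. Using Arm 1 alone as comparator changes nothing, because Arm 1 also receives integration at month 6.
- Rollout: all clinics at month 6 (Section 5.5).
- Calendar check: Section 17.1 counts data to December 31, 2020 as about 4 months after the start. The start is then about September 2020, month 6 about the end of February 2021, and month 12 about the end of August 2021. This fits Revision 4 of February 24, 2021.
- The plan states no effect size, SD or power for satisfaction. Section 17.2 covers prescribing only, so there is no planned figure to reproduce.

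**Months of integrated access at each survey**

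| Arms | Month 0 | Month 12, Section 5.1 design | Month 12, Section 5.5 |
|---|---|---|---|
| 3+4 | about 0 | 12 | 12 |
| 1+2 | about 0 | 0 | about 6 |

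**What the interaction estimates.** Let D(m) be the effect on mean satisfaction of m months of integrated access, with D(0) = 0. Leave the reminder aside for now. Time trends common to all arms cancel. With x months of access in Arms 1+2 at follow-up,

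expected interaction = [D(12) − D(0)] − [D(x) − D(0)] = D(12) − D(x).

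Under Section 5.1, x = 0 and the target is D(12). Under Section 5.5, x is about 6 and the target is D(12) − D(6). The retained share is [D(12) − D(6)] / D(12).

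| Assumed shape of D(m) | D(6) | D(12) | D(12) − D(6) | Share kept |
|---|---|---|---|---|
| Immediate, sustained | 1 | 1 | 0 | 0% |
| Saturating, 1 − 0.5^(m/1) | 0.984 | 1.000 | 0.015 | 1.5% |
| Saturating, 1 − 0.5^(m/3) | 0.750 | 0.938 | 0.188 | 20% |
| Saturating, 1 − 0.5^(m/6) | 0.500 | 0.750 | 0.250 | 33% |
| Linear, m/12 | 0.500 | 1.000 | 0.500 | 50% |
| Immediate then waning, 0.5^(m/6) | 0.500 | 0.250 | −0.250 | −100% |

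These shapes are my assumptions. An effect that accelerated with time would keep more than half.

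**The reminder.** Set B consists of integrated access and a reminder (Section 4.1). Section 5.5 does not say whether the reminder was opened with the integration. Let R(m) be the reminder's effect. Assume that it adds to D(m) and stays on in Arms 3+4, since Section 5.5 cancels the second randomization. The interaction gains R(12) − R(6) if the reminder was opened to all, and R(12) if it was not. Neither case gives the full Set B effect, D(12) + R(12).

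**Can another window recover the comparison?** Not for the survey. D(6) − D(0) would need a wave at or before month 6, and none exists. PDMP checking is different. Its counts are monthly, from August 2019 to September 2021 (Section 5.2), and can be cut at the rollout. Yet Section 17.3 fits that model to 12 months post-intervention and makes no such cut.

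**Set A.** The contrast of Arms 2+4 with Arms 1+3 keeps clinics without choice architecture at month 12. It is estimated with PMP integration in every clinic from month 6.

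**The case against.** The best defence has four parts.

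First, the interaction is still a valid randomized comparison by assigned arm, and the survey paragraph never says that it measures integration against usual care. The first half stands: the number can be reported. The second does not rescue the plan, because Section 17.3 calls the matching interaction the measure of the intervention effect and gives the survey no other meaning.

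Second, the comparator was lost by following the Data Monitoring Committee, an option that Section 17.1 foresaw. That is true, and the decision is not criticized here. The analysis text needs to follow it.

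Third, the arms may still differ in more than duration. Sections 5.1 and 17.1 treat integration and the reminder as separable. If only integration was opened, the contrast still carries reminder against no reminder. This stands. A reader might infer that all clinics had an identical tool from month 6, and Section 5.5 does not establish that.

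Fourth, this is one factor of one secondary outcome, and the PDMP-checking model has the same problem with more at stake. This also stands, so the fix covers both. Only the survey is beyond repair by a cut at month 6.

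**Conclusion.** For the PMP factor, the survey interaction compares about 12 with about 6 months of integrated access, plus the reminder if that was withheld from Arms 1 and 2. It does not estimate PMP integration against no integration, and no reanalysis of two waves can. This holds for any shape of the effect. It rests only on the survey dates and the month-6 rollout.

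The size is not known. Under the assumed shapes, and if the reminder was opened as well, the contrast keeps 0% to 50% of the effect, and the sign reverses if the effect wanes.

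Three stronger readings go beyond the documents:
- **The estimate is necessarily biased toward zero.** A reader might infer this, but the waning case gives −100%, so the direction is not fixed.
- **A stated loss of power.** If 80% power for the full effect is assumed (two-sided 0.05), the non-centrality is 1.960 + 0.842 = 2.802. Keeping half gives 1.401 and power of 29%; keeping none gives 5%. The loss of 51 to 75 points comes from an assumed starting power and two chosen shapes. It is not a property of this trial.
- **The May 2022 revision reviewed this model and left it alone.** The revision history records only minor analysis changes without naming them, and the preceding text is not available. What can be said is that the current text does not address the rollout.

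**What to change.** 1. In Section 5.5, state whether the reminder was opened at month 6 along with the integration. Also reconcile the arm numbers: Section 5.5 places choice architecture in Arms 3 and 4, while Sections 5.1 and 17.3 place it in Arms 2 and 4.
2. In the survey paragraph of Section 17.3, keep the arm-by-wave interaction as the test of Set A (Arms 2+4 against 1+3, as Section 17.3 has it). State that every clinic has PMP integration at follow-up.
3. Define the Arms 3+4 against 1+2 survey contrast as early versus delayed PMP integration, and name the reminder difference if it applies. Report it descriptively. State that it does not estimate the effect against no integration and that a null is not evidence of no effect.
4. Base PCP-level conclusions on integration against no integration on outcomes before month 6. For that contrast, limit the PDMP-checking model to the months before the rollout.

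The cost is plan wording, with no new data. The trial gives up a claim about satisfaction that its data cannot support. The PDMP-checking contrast uses about 6 post-intervention months in place of 12.
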